### **8.1.1 Unanticipated Problems**

The Office for Human Research Protections (OHRP) considers unanticipated problems (UPs) involving risks to participants or others to include, in general, any incident, experience, or outcome that meets **all** of the following criteria:

- Unexpected (in terms of nature, severity, or frequency) given (a) the research procedures that are described in the protocol-related documents, such as the IRB-approved research protocol and informed consent document and (b) the characteristics of the participant population being studied;
- Related or possibly related to participation in the research (in the guidance document, possibly related means there is a reasonable possibility that the incident, experience, or outcome may have been caused by the procedures involved in the research);
- Suggests that the research places participants or others at a greater risk of harm (including physical, psychological, economic, or social harm) than was previously known or recognized.

### **8.1.2 Adverse Events**

The International Conference on Harmonisation (ICH) Guideline for Good Clinical Practice (GCP) defines an AE as "any untoward medical occurrence in a patient or clinical investigation

---

subject administered a pharmaceutical product and which does not necessarily have a causal relationship with this treatment. An adverse event (AE) can therefore be any unfavorable and unintended sign (including an abnormal laboratory finding), symptom, or disease temporally associated with the use of a medicinal (investigational) product, whether or not related to the medicinal (investigational) product.”

### **8.1.3 Serious Adverse Events**

A serious adverse event (SAE) is one that meets one or more of the following criteria:

- Results in death
- Is life-threatening (places the participant at immediate risk of death from the event as it occurred)
- Results in inpatient hospitalization or prolongation of existing hospitalization
- Results in a persistent or significant disability or incapacity
- Results in a congenital anomaly or birth defect
- An important medical event that may not result in death, be life-threatening, or require hospitalization may be considered an SAE when, based upon appropriate medical judgment, the event may jeopardize the participant and may require medical or surgical intervention to prevent one of the outcomes listed in this definition.

## **8.2 Time Period and Frequency for Event Assessment and Follow-Up**

Unanticipated problems will be recorded in the data collection system throughout the study.

The PI will record all reportable events with start dates occurring any time after informed consent is obtained until 7 (for nonserious AEs) or 30 days (for SAEs) after the last day of study participation. At each study visit, the investigator will inquire about the occurrence of AE/SAEs since the last visit. Events will be followed for outcome information until the event returns to baseline, resolves, or stabilizes. If the AE does not meet these outcomes within 30 days after discontinuation or the end of the study, the participant will be referred to an appropriate practitioner for continued care.

## **8.3 Characteristics of Adverse Events**

### **8.3.1 Relationship to Study Drug**

The PI will make the determination of the relationship of an AE to the study drug according to the following guidelines:

1. Related (Possible, Probable, Definite)
  - a. The event is known to occur with the study intervention.

- b. There is a temporal relationship between the intervention and event onset.
- c. The event abates when the intervention is discontinued.
- d. The event reappears upon a re-challenge with the intervention.

2. Not Related (Unlikely, Not Related)

- a. There is no temporal relationship between the intervention and event onset.
- b. An alternate etiology has been established.

### **8.3.2 Relationship to Study Procedures**

The same procedure as described in Section 8.3.1 for determining the relatedness of an AE to study drug will be used to determine its relatedness to a study procedure.

### **8.3.3 Expectedness of AEs**

The NIDCR Medical Monitor and the Study PI will be responsible for determining whether an AE is expected or unexpected. An AE will be considered unexpected if the nature, severity, or frequency of the event is not consistent with the risk information described in the protocol or the Investigator's Brochure or discussed with the participant during the informed consent process.

### **8.3.4 Severity of Event**

Adverse events will be graded on a scale from 1 to 5 according to the following standards from the National Cancer Institute's *Common Terminology Criteria for Adverse Events* (v 4.0), which may be found in its entirety at <http://ctep.cancer.gov/reporting/ctc.html>:

- Grade 1 = mild AE
- Grade 2 = moderate AE
- Grade 3 = severe or medically significant AE
- Grade 4 = life-threatening AE
- Grade 5 = death

## **8.4 Reporting Procedures**

### **8.4.1 Adverse Event Reporting to IRB and NIDCR**

Study staff will report AEs on a case report form in the EDC system. Adverse events will be reported to the IRBs and DSMB according to guidelines established by those boards.

#### **8.4.2 Unanticipated Problem Reporting to IRB and NIDCR**

Incidents or events that meet the OHRP criteria for unanticipated problems require the creation and completion of an unanticipated problem report form within the EDC system. If an unanticipated problem also meets the criteria for an AE or SAE, it will be reported as an unanticipated problem and an AE or SAE. The OHRP recommends that investigators include the following information when reporting an adverse event, or any other incident, experience, or outcome as an unanticipated problem to the IRB:

- Appropriate identifying information for the research protocol, such as the title, investigator's name, and the IRB project number
- A detailed description of the adverse event, incident, experience, or outcome
- An explanation of the basis for determining that the adverse event, incident, experience, or outcome represents an unanticipated problem
- A description of any changes to the protocol or other corrective actions that have been taken or are proposed in response to the unanticipated problem

To satisfy the requirement for prompt reporting, unanticipated problems will be reported using the following timeline:

- Unanticipated problems that are SAEs will be reported to the IRB and to NIDCR within 1 week of the investigator becoming aware of the event.
- Any other UP will be reported to the IRB and to NIDCR within 2 weeks of the investigator becoming aware of the problem.
- All UPs should be reported to appropriate institutional officials (as required by an institution's written reporting procedures), the supporting agency head (or designee), and OHRP within one month of the IRB's receipt of the report of the problem from the investigator.

All unanticipated problems will be submitted on the UP form within the EDC system to NIDCR's centralized reporting system via Rho Product Safety. However, in cases when the EDC system is not available, the investigator may report the UP by fax or email:

- Product Safety Fax Line (US): [name]
- Product Safety Email: [rho\\[contact]](mailto:[contact])

General questions about UP reporting can be directed to the Rho Product Safety Help Line (available 8:00AM – 5:00PM Eastern Time):

- US: [name]

#### **8.4.3 Serious Adverse Event Reporting to NIDCR**

Any AE meeting the specified serious adverse event criteria will be submitted on an SAE form within the EDC system to NIDCR's centralized safety system via Rho Product Safety. However, in cases when the EDC system is not available, the investigator may report the SAE by fax or email. Once submitted, Rho Product Safety will send a confirmation email to the investigator

---

within 1 business day. The investigator should contact Rho Product Safety if this confirmation is not received. This process applies to both initial and follow-up SAE reports.

SAE Reporting Contact Information:

- Product Safety Fax Line (US): [name]
- Product Safety Email: [rho\\[contact]](mailto:[contact])

General questions about SAE reporting can be directed to the Rho Product Safety Help Line (available 8:00AM – 5:00PM Eastern Time):

- US: [name]

The study clinician will complete a Serious Adverse Event Form and submit within the EDC system (or via fax or email if the EDC system is not available) within the following timelines:

- All deaths and immediately life-threatening events, whether related or unrelated to the study drug, will be recorded on the Serious Adverse Event Form and submitted to Product Safety within 24 hours of site awareness.
- Serious adverse events other than death and immediately life-threatening events, regardless of relationship to the study drug, will be reported within 72 hours of site awareness.

All SAEs will be followed until resolution or stabilization.

Serious adverse events will be reported to the IRBs and DSMB according to guidelines established by those boards.

#### **8.4.4 Reporting Abnormal Clinical Findings**

Any clinically significant worsening of a medical condition (other than TMD) established at baseline or the development of any new clinically significant medical condition during the study will be considered an AE and will be reported as described previously.

#### **8.4.5 Reporting of Pregnancy**

Pregnancy will be recorded on a case report form within the EDC system if it begins any time during the study. Pregnancy will not be regarded as an SAE unless there is suspicion that the study drug may have interfered with the effectiveness of a contraceptive medication and the event meets the criteria for an unanticipated problem. Results of all positive pregnancy tests will be given to the participant and/or her legally authorized representative, as appropriate.

Participants who become pregnant while participating in the study will be discontinued from the study and referred for appropriate care. If a participant becomes pregnant while receiving the study drug, she will be followed for safety until a pregnancy outcome is reached. If the pregnancy results in an outcome other than a normal birth or elective abortion of a healthy fetus, it will be reported as an SAE.

---

## 8.5 Halting Rules

See Section 4.4.6, Suspension or Termination of the Study.

## 9 STUDY OVERSIGHT

In addition to the PI's responsibility for oversight, safety oversight will be under the direction of a DSMB convened by NIDCR. The DSMB is composed of members with expertise in pain management. The DSMB will meet periodically or as needed to assess safety and efficacy data, study progress, and data integrity for the study. If safety concerns arise, more frequent meetings may be held. The DSMB will operate under the rules of an NIDCR-approved charter that will be written at the organizational meeting of the DSMB. At this time, most data elements that the DSMB needs to assess will be clearly defined. The DSMB will provide recommendations to the NIDCR. The PI will be responsible for responding to inquiries and recommendations made by the DSMB.

## 10 CLINICAL MONITORING

Clinical site monitoring is conducted to ensure that the rights of human participants are protected, that the study is implemented in accordance with the protocol and/or other operating procedures, and that the quality and integrity of study data and data collection methods are maintained. Monitoring for this study will be performed by NIDCR's Clinical Research Operations and Management Support (CROMS) contractor. The monitor will evaluate study processes and documentation based on NIDCR standards and the ICH E6: GCP guidelines.

Details of clinical site monitoring will be documented in a Clinical Monitoring Plan (CMP) developed by the CROMS contractor, in collaboration with the NIDCR Office of Clinical Trials and Operations Management (OCTOM) and the NIDCR Program Official. The CMP will specify the frequency of monitoring, monitoring procedures, the level of clinical site monitoring activities (e.g., the percentage of participant data to be reviewed), and the distribution of monitoring reports. Some monitoring activities may be performed remotely, while others will take place at the study site(s). Staff from the CROMS contractor will conduct monitoring activities and provide reports of the findings and associated action items in accordance with the details described in the CMP. Documentation of monitoring activities and findings will be provided to the site study team, the study PIs, OCTOM, and the NIDCR. The NIDCR reserves the right to conduct independent audits as necessary.

[figure not shown]
## 11 STATISTICAL CONSIDERATIONS

### 11.1 Study Hypotheses

#### 11.1.1 Primary Hypothesis

We hypothesize that among this study population of participants with TMD, the net change in the mean pain index at Visit 4 will be greater in the propranolol-treated arm than in the placebo-treated arm. Net change is defined as the difference between the participant's mean pain index at Visit 1 and each subsequent visit. Efficacy of propranolol is defined as the difference between the propranolol and placebo arms in the mean net change. Figure 2 uses hypothetical data to illustrate how the primary hypothesis is restricted to efficacy at Visit 4 ( $\Delta V4$ ).

**Figure 2. Hypothetical Data Illustrating the Primary Hypothesis**

#### 11.1.2 Secondary Hypothesis

- We hypothesize that among this study population of participants with TMD, the efficacy of propranolol will vary according to the number of LPS haplotypes of the COMT gene.
- We hypothesize that, compared with participants in the placebo-treated arm, participants in the propranolol-treated arm will have more favorable secondary endpoints, namely: (1) reduction in additional ratings of pain; (2) reduction in examiner-assessed levels of

pain sensitivity (pressure and heat pain sensitivity); (3) better participant ratings of physical function, emotional function, and global improvement; and (4) less frequent use of rescue medications and over-the-counter medications for pain.

### 11.1.3 Exploratory Hypotheses

- We hypothesize that efficacy of propranolol will vary according to genetic variants including, but not limited to the *COMT* gene promoter and the *ADRB2* and *ADRB3* genes.
- We hypothesize that efficacy of propranolol will vary according to phenotypic characteristics.

## 11.2 Sample Size Considerations

This study plans to randomize 200 participants, which will provide 94% power (alpha = 0.05) to detect a difference between a 27% reduction in pain index in the propranolol arm and a 9% reduction in the placebo arm (primary hypothesis). Assuming haplotype distributions and within-haplotype treatment effects that are similar to those observed in the pilot study, the same sample size would provide 61% power (alpha = 0.05) to detect an interaction between haplotype and treatment group (secondary hypothesis). The assumptions for these power calculations are shown in the following table. Power calculations were made using the GLMPOWER procedure in SAS, which assumes a data structure of one observation per person. This is a simplification of the situation that will occur with the linear mixed model described in Section 11.4.1 in which efficacy will be evaluated using a data structure in which most participants will have three observations per person. The simplified power calculations are shown here because conventional software for power calculations does not deal with the more complex situation of linear mixed models.

		Primary Hypothesis		Secondary Hypothesis					
COMT haplotype		All haplotypes		0 LPS copies		1 LPS copy		2 LPS copies	
Treatment arm		Drug	Placebo	Drug	Placebo	Drug	Placebo	Drug	Placebo
% of participants (N = 200)		50%	50%	15%	15%	25%	25%	10%	10%
Mean baseline pain index		3000	3000	3000	3000	3000	3000	3000	3000
Net change		-810	-270	-1350	-270	-810	-270	-270	-270
Percentage change		-27	-9	-45	-9	-27	-9	-9	-9

\* LPS stands for low pain sensitive, one of the major haplotypes of *COMT*. The standard deviation for the mean baseline pain index is estimated to be 1190. The net change takes into account a 10% lost-to-follow-up rate and imputation using the last observation carried forward approach.

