The primary endpoint will be the weekly pain index derived from the Daily Symptom Diary. Efficacy will be evaluated as the difference between the propranolol and placebo arms in the mean change in the pain index during treatment. In addition, variation in efficacy will be compared between groups of participants classified according to polymorphisms in the coding region of the *COMT* gene.

Enrollment will not be stratified according to *COMT* genotype because in the pilot study sample, the haplotype variants were sufficiently distributed for statistical evaluation of a treatment-haplotype interaction without stratified randomization. In the pilot study, 30% of participants had no copies of the LPS haplotype, 50% had one copy, and 20% had two copies. Stratification by *COMT* genotype would significantly increase the complexity of enrollment and could delay the start of treatment for participants while their DNA test results were pending. The DNA analyses will be conducted after all participants have been enrolled.

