### 11.4.1 Analysis of the Primary Hypothesis

The primary statistical analysis to evaluate the primary hypothesis will use all data from the intention-to-treat analytical sample in a linear mixed model. During the analysis of the primary hypothesis, treatment allocation will be masked (i.e., groups will be labeled A and B). Treatment allocation will be unmasked for further analyses.

---

The dependent variable will be the participant's change in the weekly pain index, computed as the weekly pain index at the follow-up visit (i.e., at Visit 2, Visit 3, or Visit 4) minus the Visit 1 weekly pain index. Explanatory variables will comprise fixed factors and a continuous covariate. The fixed factors will include the following: (a) treatment allocation (two categories) (b) visit sequence (three categories); (c) interaction of treatment allocation and visit sequence (two dummy variables); and (d) covariates of study site (three categories), sex (two categories) and race/ethnicity (probably three categories: non-Hispanic White, non-Hispanic Black, and other/multiple racial or ethnic groups – the final number of conditions will be dictated by the frequency distribution of race/ethnicity in the study sample). The baseline score collected at Visit 1 will be the continuous covariate, modeled as a fixed effect. The study participant will be modeled as a random factor.

In a linear mixed model containing all predictor variables including the interaction terms for visit and treatment allocation, the primary treatment effect will be tested at Visit 4. The null hypothesis of no treatment effect will be rejected if the P-value at Visit 4 is  $\leq 0.05$ . For descriptive purposes (and regardless of the P-value for efficacy at Visit 4), efficacy estimates at each visit (2, 3 and 4) will be described in terms of adjusted means and 95% confidence intervals.

If the propranolol treatment arm has a greater reduction in the weekly pain index than the placebo arm at Visit 4, a threshold of "responder analysis" will be undertaken to estimate the odds of at least a 30% reduction, relative to Visit 1, in the pain index at Visit 4. Likewise, another threshold of responder analysis will describe the odds of experiencing at least a 50% reduction. These estimates will be calculated from a logistic model in which the dependent variable is a binary variable that dichotomizes the change score at the appropriate threshold (i.e.,  $\geq 30\%$  or  $\geq 50\%$ ).

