2.6 Sample Size Determination

This study plans to randomize 200 participants, which will provide 94% power (alpha = 0.05) to detect a difference between a 27% reduction in pain intensity in the propranolol arm and a 9% reduction in the placebo arm (primary hypothesis). Assuming haplotype distributions and within-haplotype treatment effects that are similar to those observed in the pilot study, the same sample size would provide 61% power (alpha = 0.05) to detect an interaction between haplotype and treatment group (secondary hypothesis).

Power calculations were made using the GLMPOWER procedure in SAS, which assumes a data structure of one observation per person. This is a simplification of the situation that will occur with the linear mixed model, described in Section 10.4.1, where efficacy will be evaluated using a data structure where most participants will have three observations per person. The simplified power calculations are shown here because conventional software for power calculations does not deal with the more complex situation of linear mixed models.

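### The inputs in Protocol 11.2 give about 89% two-sided power for 27% vs 9%, not 94%, and the table's haplotype columns average to 28.8%, not 27%

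*Protocol*

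**What the plan says.** Protocol 11.2 gives the primary power for 200 randomized participants, "which will provide 94% power (alpha = 0.05) to detect a difference between a 27% reduction in pain index in the propranolol arm", set against 9% on placebo. For the secondary hypothesis it says that "the same sample size would provide 61% power (alpha = 0.05) to detect an interaction between haplotype and treatment group". Both come from SAS GLMPOWER with one observation per person.

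The accompanying table assumes a baseline index of 3000. The all-haplotypes columns show net changes of -810 (drug) and -270 (placebo). The columns for 0, 1 and 2 LPS copies show -1350, -810 and -270 on drug, and -270 throughout on placebo, with 15%, 25% and 10% of participants in each arm-by-haplotype cell. Protocol 3 reports the same split from the pilot: "30% of participants had no copies of the LPS haplotype, 50% had one copy, and 20% had two copies".

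The table footnote adds: "The standard deviation for the mean baseline pain index is estimated to be 1190". It also says: "The net change takes into account a 10% lost-to-follow-up rate and imputation using the last observation carried forward approach".

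On the test itself, Protocol 11.1.1 words the hypothesis directionally: "the net change in the mean pain index at Visit 4 will be greater in the propranolol-treated arm than in the placebo-treated arm". Protocol 11.4.1 states the decision rule: "The null hypothesis of no treatment effect will be rejected if the P-value at Visit 4 is" at or below 0.05, with 95% confidence intervals for the visit estimates. SAP 2.6 repeats the 94%, but for a "27% reduction in pain intensity in the propranolol arm".

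**The concern.** The 94% is the only power figure for the primary hypothesis, and the protocol says that the table holds the assumptions behind it. A reader who puts the table's values into a standard two-sample calculation gets a lower figure. The same reader finds that the all-haplotypes effect is not the average of the haplotype effects, although both describe the same 200 people.

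A null result would be read against 94% power for 27% vs 9%. On the stated inputs, the type II error is about 11% rather than 6%. As written, it is also unclear which effect, which SD and which sidedness the 94% refers to.

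**Working it through.** **Inputs (Protocol 11.2).** 100 per arm; difference 810 - 270 = 540; SD 1190; alpha 0.05; one observation per person. For now, 1190 is taken as the SD of the net change.

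**1. Primary power as stated.** Noncentrality = (difference / SD) × sqrt(n/2), with n = 100 per arm and 198 degrees of freedom.

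- 540 / 1190 × sqrt(50) = 3.209. Noncentral t, two-sided 0.05: **89.1%** (normal approximation 89.4%).
- Reaching 94% two-sided at 540 would need about 120 per arm, or an SD of about 1081.
- The 10% loss is not the cause. The footnote says that it is already in the net change, and 90 per arm would lower power to 85.7%.

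**2. Consistency of the table.** Weight the drug-arm haplotype columns by 30/50/20%:

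- 0.3 × (-1350) + 0.5 × (-810) + 0.2 × (-270) = -405 - 405 - 54 = **-864**.
- 864 / 3000 = **28.8%**, where the all-haplotypes column has -810, or 27%.
- Difference from placebo: 864 - 270 = **594**.

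This step needs no assumption about SD or sidedness.

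**3. Where the 94% may come from.** 594 / 1190 × sqrt(50) = 3.530, which gives **94.0%** two-sided.

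**4. Check against the second stated power.** With cells of 30, 50 and 20 per arm, treatment effects are 1080, 540 and 0, a slope of 540 per LPS copy. The mean copy number is 0.9, and the sum of squares per arm is 30 × 0.81 + 50 × 0.01 + 20 × 1.21 = 49.

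- Interaction noncentrality = 540² × (49/2) / 1190² = 5.045.
- A 1-df linear interaction has **60.8%** power two-sided (stated: 61%). A 2-df categorical interaction has 50.1%.

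One setting (two-sided 0.05, N = 200, SD 1190, haplotype columns) therefore returns both published powers.

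**5. Rival readings.**

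| Reading | Primary | Interaction, 1 df | Interaction, 2 df |
|---|---|---|---|
| Stated in Protocol 11.2 | 94% | 61% (df not stated) | 61% (df not stated) |
| Two-sided, SD 1190, difference 594 | 94.0% | 60.8% | 50.1% |
| Two-sided, SD 1190, difference 540 | 89.1% | 60.8% | 50.1% |
| One-sided 5%, SD 1190, difference 540 | 94.0% | 72.4% | 62.7% (alpha 0.10 as a loose analogue) |
| Two-sided, SD 1081, difference 540 | 94.0% | 69.2% | 58.6% |

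**6. If 1190 is only the baseline SD.** The documents give no SD of change and no baseline-to-follow-up correlation r. Assume equal SDs at both times. An unadjusted change score then has SD 1190 × sqrt(2(1 - r)), and a baseline-adjusted analysis has SD 1190 × sqrt(1 - r²). Two-sided power at 540:

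| Assumed r | SD of change | Power | Baseline-adjusted SD | Power |
|---|---|---|---|---|
| 0.4 | 1304 | 83.0% | 1091 | 93.6% |
| 0.5 | 1190 | 89.1% | 1031 | 95.8% |
| 0.6 | 1064 | 94.6% | 952 | 97.9% |

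**The case against.** The strongest objection is that the stated inputs do not fix the power. The footnote labels 1190 a baseline SD, the planned analysis adjusts for baseline, and r of about 0.42 would bring 27% vs 9% to 94%. Sidedness is also unstated, the hypothesis is directional, and a one-sided 5% test at 540 gives 94.0%. The interaction test could have had 2 df, since Protocol 11.4.2 leaves linear or categorical coding to Akaike's criterion. The rival readings then miss 61% by only about 2 points (58.6% and 62.7%). The mismatch in the table is 1.8 percentage points, and 89% is still good power.

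Part of this stands. The 89% depends on 1190 being the SD of change. The source of the 94% is inferred, and against a 2-df test the rivals are excluded less firmly than against a linear one.

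The rest does not rescue the text. No correlation or smaller SD appears in either document. Neither document plans a one-sided test, and the decision rule rejects a null of no effect at 0.05 alongside 95% intervals. No rival returns both published powers as closely as the haplotype-column reading, and none removes the conflict between 27% and 28.8%.

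**Conclusion.** The concern holds. On the inputs in Protocol 11.2, power for 27% vs 9% is 89.1% two-sided, about 5 points below the stated 94%. This rests on a two-sided 0.05 test and on 1190 being the SD of the analysed net change. If 1190 is only the baseline SD, the illustrative range is 83.0% to 97.9% for r from 0.4 to 0.6, so the 94% can be neither confirmed nor reproduced from the documents.

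The conflict between -810 and -864 in the table is plain arithmetic and depends on none of this. The most likely explanation is that 94% was computed for 28.8% vs 9% and then attached to 27% vs 9%. This is an error of labelling and consistency in a headline design figure; it does not make the trial undersized.

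**What to change.** In Protocol 11.2 and SAP 2.6:

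1. State that the power calculation is two-sided, if that is what was run.
2. State whether 1190 is the SD of the baseline index or of the net change. If baseline, give the SD of change or the assumed correlation.
3. If 1190 is the SD of change, either restate power as 89% for 27% vs 9% (difference 540) or attach 94% to 28.8% vs 9% (difference 594). If it is not, recompute from the SD given under item 2.
4. Make the all-haplotypes column agree with the haplotype columns, and say whether the 61% is for a linear (1-df) or a categorical (2-df) interaction.

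Two small additions belong in the same edit. SAP 2.6 should say pain index rather than pain intensity, which is a separate secondary outcome. The text should also note that the planning net changes assume last observation carried forward with 10% loss, whereas SAP 8.1 uses a mixed model without imputation.

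The cost is wording in two sections. The sample size, the analysis and the decision rule do not change.
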